#### **Limitations and Alternative Design**

The use of peripheral measures rather than measurement of cytokines or biochemical markers in the cerebrospinal fluid (CSF) is a limitation, however, the risks and discomfort involved in CSF measurements is not warranted without stronger justification. The central action of proinflammatory cytokines on the hypothalamic-pituitary-adrenal (HPA) axis has been suggested to be a risk factor for MDD [111]. However, data suggest that the HPA axis function is not markedly altered in HD patients [112, 113]. TNF- $\alpha$  antagonists [114] could be used to test the hypothesis that TNF- $\alpha$  contributes to depressive and cognitive symptoms. However, these compounds are expensive, difficult to administer, and have potentially serious adverse effects [115].

# Data Analysis, Statistical Considerations, and Testing of Hypotheses:

Determination of Sample Size: Hypothesis 1 concerns within-treatment group improvement of

Version #: 17, IRB #203076

PI: [name]

depression. With four post-baseline measures, calculation of power requires an estimate of the matrix of correlations among the repeated measures. We specified a medium effect size averaged across the postbaseline measures (Cohen's d=0.5 SD, 1988), unadjusted alpha of 0.05. We specified compound symmetry among the measures with r=0.50 because the measurements are relatively close in time. With these specifications, it is possible to calculate the standard error of the difference between baseline and the average of the post-baseline measures. With N=20, IBM SamplePower3's (IBM SPSS, 2000) module for the t-test for paired observations indicates power=0.78 with N=20. We confirmed this result with a simulation with 1000 datasets with the structure described, performing mixed effects analyses as described below. The simulation yielded an empirical power estimate of 0.79 for Hypothesis 1. We also evaluated a banded covariance structure in which the correlations fell off from .50 to .32 over time, and found that yielded power=0.75. Hypothesis 2 concerns between group differences. Power was calculated using Hedeker's RMASS2 software for mixed models with longitudinal data. Specifications were as above but the effect size was adjusted for the use of a baseline covariate and the design involves two groups of N=20 each assessed at four occasions. In this case, power is 0.80 to detect a standardized mean difference (Cohen's d) of 0.6. This is slightly larger than the conventional medium effect size of d=0.50. The analyses for Hypothesis 3 involves using the TRP/LNAA ratio as a covariate in mixed effects regression models with the same design structure and analytic plan as the between-groups models for Hypothesis 2. Converting Cohen's d to the correlation coefficient equivalent, d=.6 is roughly equal to r=.30. Cohen's convention for a medium correlation. Evidence that these assumptions about effect sizes are probably quite conservative can be found in previously described effects of bupropion [68, 70, 90, 116-120] and fluoxetine [28, 60, 104, 116, 121] on symptoms of major depression, cognition, and inflammation.

General Methods: Given that a primary goal of the current study is to obtain data to justify and support the feasibility of a future definitive trial, a variety of data necessary for this, including data on tolerability and safety (see below), will be obtained. For example, subject disposition will be summarized with a table indicating the number of subjects screened, the number of screen failures by reason, the number enrolled, the number who dropped out (by reason), and the number completing the study. Random double-blind assignment of patients to fluoxetine or bupropion is expected to yield similar distributions of measured and unmeasured variables of interest. This design provides a strong basis for making inferences about causal relationships between variables by controlling a priori for a wide range of patient and situational factors, thereby increasing the validity of estimates and inferential tests. In betweengroups analyses, variables that are related to outcome which differ between groups will be included as predictors in a logit model predicting group assignment, and the predicted values of this model will be incorporated as a covariate in all subsequent analyses. This includes factors that could influence treatment response [125-127], including number of prior episodes (>2 or not), treatment response vs. remission during treatment, and sex [128]. Continuously distributed outcomes will be summarized with the sample size, mean, standard deviation, median, minimum and maximum and categorical or binary outcomes with counts and percentages. Distributions will be examined to identify potentially influential observations (outliers) and suggest transforms (e.g., log) to normalize. The final report containing formatted tables and embedded graphics will be produced in Microsoft Word directly from the database using the SAS Output Delivery System. Analyses will use all subjects with usable data. All statistical testing will be two-sided with a significance level of 5%. The Holm-Bonferroni step down method will be applied as necessary to correct for multiple testing. SAS Version 9.2 for Windows (SAS Institute, Cary, North Carolina) will be used throughout.

Tolerability and Safety: We will determine incidence rates for all adverse events and treatment emergent adverse events will be determined using the SAFTEE. Treatment emergent adverse events will be defined as those that were not present before the first administration of drug, but occurred after the first administration, or that were present before the first administration but increased in severity or frequency after the first administration. Incidence rates for all adverse event and treatment emergent adverse events will be compared between medication groups using chi-square for frequencies with any events or Poisson regression for counts of numbers of events adjusting for time at risk using log time as an offset variable. The numbers of subjects withdrawing from the study for each reason will also be compared across groups using survival analysis on time to study discontinuation.

Version #: 17, IRB #203076

PI: [name]

**Testing Hypothesis 1**. Both antidepressants will be efficacious based on change in Ham-D scores over time. The primary analyses will be mixed effects regression models with repeated measures (baseline, 1, 4, 8, 12 weeks) performed separately in the medication groups. The fixed effect is time, and the hypothesis test is an *a priori* contrast comparing the baseline value with the average of the four post-baseline values. In secondary analyses, patients will be categorized as responders and remitters, with response defined as a 50% or greater improvement in Ham-D score with total score ≤ 15 at the 12 weeks compared with baseline and remission [129] as having had a treatment response plus a final Ham-D score ≤7.

**Testing Hypothesis 2**. Changes in cognition, fatigue, and depression will be evaluated between and within treatment groups. Changes in BFI and cognition should be greater in bupropion SR-treated patients [30, 32, 89, 130-140]. These analyses will use mixed effects regression models with repeated measures. Treatment group, time and their interaction are the fixed independent variables. Change in Ham-D, BFI and cognitive dysfunction (3MS, MSIT, and n-back performance) are the time-varying dependent variables. All subscales of the BFI will be summarized by time point.

**Testing Hypothesis 3**. These analyses will measure the association between CRP, TRP availability, and quinolinic acid to Ham-D score, BFI, and cognitive measures over time. Because the effects of TRP on brain 5-HT is best estimated by the ratio of free TRP to LNAA, this ratio will be calculated and used as the primary measure of possible brain 5-HT depletion. The analyses will use mixed effects regression with time, the TRP/LNAA ratio, and their interaction as independent variables and measures of depressive symptoms (HAMD) and cognitive dysfunction (3MS, n-back accuracy, and MSIT reaction time) serving as dependent variables. Supplemental analyses will be done using the presence of residual depressive symptoms (yes: HAM-D>15; no: HAM-D<=15) and presence of cognitive impairment (yes: 3MS <80, no: 3MS ≥80), presence of dental disease (yes/ no) over time (1, 4, 8 and 12 weeks) using the generalized linear model (GEE) with the same fixed effects and binomial error.

Exploratory Analyses: Additional analyses will explore age, sex, baseline depressive symptoms (HAMD), baseline dental disease and interactions of these covariates with the fixed effects in the models described above. McNemar's test will be used to compare the proportion of subjects meeting criteria for cognitive dysfunction at baseline compared with study end, and chi-square tests to compare these proportions with population rates. Pearson correlations will be used to assess the strength of associations between variables at each assessment. Correlations between the measures of depression, cognitive function, and fatigue will be tabled and summarized with scatter plots across all time points and by time point. Exploratory analyses will also substitute individual cytokines and the ratio of pro- to anti-inflammatory cytokines for inflammation in relevant analyses and also seek to define whether there is a threshold for individual cytokines or the pro/anti-inflammatory ratio before depressive symptoms (HAM-D>8) or cognitive dysfunction occur. The threshold analysis will utilize traditional receiver-operator characteristics (ROC) analyses. Both buproprion SR and Fluoxetine are local standard practice.

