# Hypotheses:

- 1) Bupropion and fluoxetine will both show efficacy in treating MDD;
- 2) Bupropion will lead to greater improvement in cognitive dysfunction and fatigue than fluoxetine; and
- 3) Change in cognition and fatigue over time will correlate with change in C-reactive protein (CRP) and quinolinic acid and change in overall depression score will correlate with measures of TRP availability.

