# 3. Study Design

The current study proposes to randomly assign 40 CKD patients with MDD to 12 weeks of open label, flexible dose treatment with either bupropion (N=20) or fluoxetine (N=20).

[NOTE: We are requesting to enroll up to 50 subjects/with 40 completers. One of the outcome measures will be the number of weeks of treatment that a person completes. This is a preliminary feasibility and pilot study, so establishing an estimate of drop out rate will be important for when we design the "definitive" study in the future.]

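### The Hypothesis 1 test can show improvement on each drug but not efficacy, and the 0.78-0.79 given as its power is for one drug in one arm of 20, not for both drugs

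*Combined protocol and SAP*

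**What the plan says.** **The claim.** The Hypotheses section states "Bupropion and fluoxetine will both show efficacy in treating MDD". Aim 1 under Specific Aims also speaks of determining efficacy. Testing Hypothesis 1 states "Both antidepressants will be efficacious based on change in Ham-D scores over time".

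**The test.** It is a mixed model on Ham-D at baseline and weeks 1, 4, 8 and 12. A planned contrast sets baseline against the average of the four later values, "performed separately in the medication groups". Section 4 requires Ham-D above 17 at entry. There is no placebo or untreated arm.

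**More modest wording elsewhere.** Determination of Sample Size opens with "Hypothesis 1 concerns within-treatment group improvement of" depression. Section 1 predicts that both drugs will reduce symptoms relative to baseline.

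**The power.** Determination of Sample Size assumes d=0.5, compound symmetry with r=0.50, unadjusted alpha of 0.05 and N=20. It reports 0.78 from a paired t-test and then "The simulation yielded an empirical power estimate of 0.79 for Hypothesis 1". No power for success in both arms is given.

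**Numbers of patients.** Section 3 plans to "randomly assign 40 CKD patients with MDD to 12 weeks of open label" treatment, 20 per drug, and adds: "We are requesting to enroll up to 50 subjects/with 40 completers". General Methods adds: "Analyses will use all subjects with usable data".

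**The concern.** Two things do not line up.

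First, the conclusion goes further than the test. A within-arm fall in Ham-D contains any drug effect together with natural course, non-specific response and regression to the mean, and regression to the mean is to be expected when entry depends on a high score on the same scale. The randomised comparison plays no part in a test run inside each arm. The Background gives its own reason for caution: it reports several positive open-label fluoxetine studies, and one placebo-controlled trial that failed. Two significant arms reported as efficacy would pass an unsupported statement on to the definitive trial that these data are meant to justify.

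Second, a power labelled as being for Hypothesis 1 invites the reader to take 0.79 as the chance of confirming that hypothesis as worded, which is that both drugs succeed. The calculation covers one drug.

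**Working it through.** **Inputs.** From Determination of Sample Size: d=0.5, r=0.50 with compound symmetry, four post-baseline measures, N=20 and alpha 0.05. Two-sided testing comes from General Methods. The contrast comes from Testing Hypothesis 1.

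**Reproducing the stated figure (one arm), in SD units.**
- Variance of the mean of four post-baseline values: (1 + 3×0.5)/4 = 0.625.
- Variance of baseline minus that mean: 1 + 0.625 − 2×0.5 = 0.625.
- Standard error with n=20: √(0.625/20) = 0.1768.
- Noncentrality: 0.5/0.1768 = 2.828.
- Noncentral t power: 0.765 with 19 df (paired t) and 0.797 with 4×19 = 76 df (mixed model). A simulation of 20,000 datasets gave 0.762 and 0.791.

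These match the stated 0.78 and 0.79, so the stated figures are power for one drug in one arm of 20.

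**Both arms, 20 full-data patients each.** The arms are independent, so the powers multiply.
- Recomputed: 0.765² = 0.59 and 0.797² = 0.64.
- From the stated figures: 0.78² = 0.61 and 0.79² = 0.62.
- If Holm were applied across the two drugs: 0.57-0.63.

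**Both arms, 25 enrolled each.** The even split, 20 completers plus five others per arm, and ignorable dropout are assumptions. The variance of the contrast is the generalised least squares variance under the same correlation. If the five give baseline data only, it is (0.625 − 0.5²)/20 + 0.5²/25 = 0.01875 + 0.01 = 0.02875. If all 25 have full data, it is 0.625/25 = 0.025.

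| Last analysed visit of the five | Variance | Noncentrality | Both arms (24 df) | Both arms (mixed-model df) |
|---|---|---|---|---|
| Baseline | 0.02875 | 2.949 | 0.652 | 0.688 |
| Week 1 | 0.02688 | 3.050 | 0.694 | 0.729 |
| Week 4 | 0.02594 | 3.105 | 0.715 | 0.751 |
| Week 8 | 0.02537 | 3.139 | 0.728 | 0.764 |
| Week 12 (no dropout) | 0.02500 | 3.162 | 0.737 | 0.773 |

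The range is therefore about 0.65-0.77.

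**Larger effect, 20 per arm.** With d=0.6 the noncentrality is 0.6/0.1768 = 3.394. One-arm power is 0.896 (19 df) or 0.918 (76 df), so both arms give 0.80 or 0.84.

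**What significance would mean.** The d in this calculation is total change from baseline, and the test cannot tell where that change comes from. Suppose, purely as an assumption, that neither drug had a specific effect and non-specific change alone were 0.5 SD. Both arms would then be significant in 59-64% of trials, by the same arithmetic as above. At 0.4 SD it would be 33-37%, and at 0.6 SD 80-84%. The documents do not allow the actual non-specific change to be estimated.

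**The case against.** **The power scope is disclosed.** This stands. The section opens by saying that the hypothesis concerns change within a treatment group, names a paired test and N=20, and contrasts this with two groups of 20 for Hypothesis 2. A reader might infer from the gap between 0.79 and 0.6 that the sponsor miscalculated. The documents do not support that: the figures reproduce, and only the label is at issue.

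**Joint success is not a stated requirement.** This also stands. No section makes success in both arms a decision rule, and separate models suit two per-drug questions, for which 0.78-0.79 is the right figure each. It would go too far to call the trial underpowered against a criterion it set. The word 'both' in the hypothesis and again in its test still leaves the joint reading open, and the text does not resolve it.

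**The 0.6 is conditional.** It needs d=0.5 in both arms and 20 full-data patients per arm. The plan calls its effect sizes probably conservative and allows for up to 50 enrolled, so higher values are possible, as shown. A lower figure could be had by squaring the 0.75 quoted for a banded correlation structure. The exact pattern is not given, though, and plausible versions gave 0.67-0.74 rather than 0.75, so nothing is rested on it.

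**This is a pilot, and some passages are already modest.** That is true, and it limits how much is at stake. The efficacy wording remains in the aim, the hypothesis and its test.

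**The causal-inference sentence in General Methods.** A reader might take it as claiming causal status for the within-arm test. In context it follows a statement about random assignment to the two drugs and precedes one about between-group analyses, so it already refers to the randomised comparison.

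**Conclusion.** The concern holds as a mismatch between label and test, not as an arithmetic error. The firmer part does not depend on any power figure: an arm-by-arm baseline contrast with no untreated comparator, in patients selected on the outcome scale, supports a statement of improvement on each drug and not one of efficacy. It does not follow that the improvement would be mostly regression to the mean or non-specific; the documents do not settle that share.

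On power, 0.78-0.79 is correct for each drug separately. For both drugs together it is about 0.6 under the plan's inputs with 20 full-data patients per arm. The higher figures of about 0.65-0.77 and 0.80-0.84 need, respectively, 25 enrolled per arm under the stated dropout assumptions, or d=0.6 in each arm.

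**What to change.** 1. In Specific Aims (Aim 1), Hypotheses (item 1) and Testing Hypothesis 1, replace the efficacy wording with that of Section 1: each drug reduces MDD symptoms from baseline.
2. In Limitations and Alternative Design, add that there is no untreated comparator, so change within an arm cannot be attributed to the drug.
3. In Determination of Sample Size, label 0.78-0.79 as power for each drug separately, and state that the chance of both arms being significant is about 0.6 at d=0.5 with 20 per arm. If a figure for 25 enrolled per arm is added, give it as 0.65-0.77 with its dropout assumptions.

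General Methods needs no edit. The cost is a less favourable stated figure and a more modest claim, with no change to enrolment or analysis.

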Participation of an eligible subject in this clinical trial is a voluntary process. Subjects will not be coerced or influenced by the study personnel. In order to participate, subjects will have to voluntarily initiate a phone screening and subsequently come to a face-to-face consent/initial evaluation meeting. A research staff member or study investigator will conduct the consent process in order to minimize the possibility of undue influence from the treating physician on their hemodialysis team. Subjects will be informed that participation is voluntary and not participating will not affect the delivery of the routine health care. They and their treating physicians will be informed that the medications being used in the current study are routinely available and relatively inexpensive to obtain. They do not have to participate in this study to receive any of the treatment options.

Subjects are randomly assigned to open label treatment with one of two medications. Therefore, there are two groups:

- Bupropion group:
  - For patient not on hemodialysis, oral administration of bupropion SR tablet at a dose of 150 mg daily. Bupropion SR doses will be adjusted upward or downward based on tolerability and response.
  - For patient on hemodialysis or peritoneal dialysis, oral administration of bupropion SR tablet at a dose of 150 mg on the 1st and the 3rd dialysis day of each week. Bupropion SR doses will be adjusted upward or downward based on tolerability and response.
- Fluoxetine group: Oral administration of fluoxetine tablet will be started at a dose of 10 mg/day for the first week and then increased, as tolerated to 20 mg/day for weeks 2–4. After this, doses will be adjusted based on clinical response and side effects up to a maximum dose of 60 mg/daily by week 10.

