## 6. Research Plan

The current study proposes to recruit up to 50 participants in order to have 40 completers. Eligible CKD patients with MDD will be randomly assigned to 12 weeks of open label, flexible dose treatment with either Bupropion SR (N=20) or Fluoxetine (N=20). Patients will be recruited from the UAMS dialysis center or other local dialysis centers via flyers, referral by their treating physician and/or newspaper ads. Written consent will be obtained before any study procedures. Subjects are randomly assigned to open label treatment with one of the following:

• Bupropion group:

Version #: 17, IRB #203076

PI: [name]

 For patient not on hemodialysis or peritoneal, oral administration of bupropion SR tablet at a dose of 150 mg daily. Bupropion SR doses will be adjusted upward or downward based on tolerability and response.

- For patient on hemodialysis or peritoneal dialysis, oral administration of bupropion SR tablet at a dose of 150 mg on the 1st and the 3rd dialysis day of each week. Bupropion SR doses will be adjusted upward or downward based on tolerability and response.
- Fluoxetine group: Oral administration of fluoxetine tablet will be started at a dose of 10 mg/day for the
  first week and then increased, as tolerated to 20 mg/day for weeks 2–4. After this, doses will be
  adjusted based on clinical response and side effects up to a maximum dose of 60 mg/daily by week
  10.

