Participants will receive the study medication during the baseline assessment and instructed to begin the medication on day 1 (1st dialysis day) of week 1 of the study. For patient on hemodialysis or peritoneal dialysis, generic bupropion SR will be dosed at 150 mg on the 1st and the 3rd dialysis day of each week with doses adjusted upward or downward based on tolerability. The initial dose of bupropion-SR is based on the findings of Worrall et al [80], who measured plasma bupropion levels in a pharmacokinetic study of bupropion in HD patients. For patient not on hemodialysis or peritoneal dialysis, generic bupropion SR tablet will be dosed at 150 mg daily. Bupropion SR doses will be adjusted upward or downward based on tolerability and response. Fluoxetine will be started at 10 mg/day for the first week and then increased, as tolerated to 20 mg/day for weeks 2–4. After this, doses will be adjusted based on clinical response and side effects up to a maximum dose of 60 mg/daily by week 10 [62]. At the week 12 visit, the participants will stop the medication or may undergo a 1-2 week taper (depending on maintenance dose) if they are on a dose of fluoxetine that is higher than 20 mg.

Subjects will be seen during weeks 1, 2, 3, 4, 6, 8, 10, and 12 in face-to-face meetings by a rater blind to study medication and a study physician for Ham-D ratings, CGI, medication accountability, and measurement of adverse events. On weeks 5, 7, 9 and 11, subjects will come in to return the previous week's pill bottles and pick up the current week's medication. Table 1 shows study procedures. Medication will be prepared by UAMS Research Pharmacy, labeled with the directions for use and contact information, and given to participants by study staff on a weekly basis. Compliance will be monitored using the MAFV at each scheduled encounter and by analysis of antidepressant blood levels. Results of a second EKG done during week 4 will be reviewed to ensure QTc interval is less than 500 msec.

In order to control for the potential confound of chronic pain we will characterize it with the physical and psychological pain scale and with two objective measures, i.e. the pressure pain threshold and the Quantitative Sensory Test (QST).

Version #: 17, IRB #203076

PI: [name]

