# The following tools will be utilized:

- a) The Mini International Neuropsychiatric Interview (MINI) [75]. Psychiatric diagnosis will be assessed with the MINI, a widely used semi-structured interview for DSM-IV diagnoses. It has high reliability, for MDD and depressive subtypes. (Time - 30 min).
- b) The Hamilton Depression (HAM-D) Scale [76]. Depressive symptoms in all phases of this study will be measured with the 25-item version of the HAM-D. (Time – 5 minutes).
- c) The Profile of Mood States (POMS) [81, 82]. The POMS is one of the most validated measures for measuring a wide range of clinical and subclinical changes in mood. It has been studied extensively in various clinical samples including psychiatric patients as well as in cancer, drug abuse and addictions, and the broad domain of exercise, fitness, sports psychology, and sports medicine. (Time – 10 min).
- d) The Brief Fatigue Inventory (BFI) [83]: It is used to assess the severity of fatigue and the interference of fatigue with daily functioning. The interference items include general activity, mood, walking ability, normal work (includes both work outside the home and housework), relations with other people, and enjoyment of life. The interference items are measured on a 0-10 scale, with 0 being "does not interfere" and 10 being "completely interferes." (Time – 5 minutes).
- e) The Modified Mini Mental Status (3MS) Examination [78]: The 3MS Examination is a validated screening tool to evaluate global cognitive function with components for orientation to time and place. attention, language, immediate recall, short-term verbal memory, calculation, construct ability, and memory. [84]. (Time – 8 minutes).

Version #: 17. IRB #203076

PI: [name]

f) Delay discounting task. It is a decision making task. Subjects will be presented a series of trials in which they will choose between a set of hypothetical rewards or losses to be received in variable time spans. Smaller sooner (SS) hypothetical reward/loss (\$X) received today or a larger later reward/loss (LL) (\$1000) received at a future delay (1wk, 1mo, 6mo, 1yr). The value of the SS award will be titrated with participant responses so that an equal number of SS and LL choices are selected for each delay. Time - 5 minutes [144].

g) Multi-Source
Interference Test
(MSIT): MSIT is a nonverbal test of attentional
conflict which combines
elements of the Stroop,

Table 1. Study Procedures									
Measures	Week of Study								

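### General Methods calls assignment double-blind in an open-label trial, and Hypothesis 1 would read efficacy from a change from baseline that has no control

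*Combined protocol and SAP*

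**What the plan says.** **Blinding.** In the analysis section, the General Methods paragraph says: "Random double-blind assignment of patients to fluoxetine or bupropion is expected to yield similar distributions of measured and unmeasured variables of interest". The next sentence begins: "This design provides a strong basis for making inferences about causal relationships between variables", and goes on to credit control in advance over patient and situational factors.

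The design sections say otherwise. Section 3 proposes random assignment to 12 weeks of open-label, flexible-dose treatment. Section 5 (Consent Process) says: "Subjects are randomly assigned to open label treatment with one of two medications". Section 6 (Research Plan) repeats: "Subjects are randomly assigned to open label treatment with one of the following". The one blinding measure is also in Section 6, where patients are seen "by a rater blind to study medication and a study physician for Ham-D ratings, CGI, medication accountability, and measurement of adverse events". No matching or dummy medication is described.

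**Hypothesis 1.** Aim 1 is to determine the efficacy of both drugs. The listed hypothesis is that both will show efficacy. The Testing Hypothesis 1 paragraph says both will be efficacious, judged on Ham-D change over time. The primary analysis is a mixed model fitted separately in each arm, with a contrast of baseline against the average of the four post-baseline values. Both arms receive an active drug. Entry requires a Ham-D score above 17 (Section 4).

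**Hypothesis 2.** This is the between-arm comparison of Ham-D, fatigue and cognition. The plan predicts a direction: "Changes in BFI and cognition should be greater in bupropion SR-treated patients".

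**The concern.** There are two separate faults.

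First, the analysis section states a design property that the trial does not have. If the sentence is carried into a report, readers will take it that patients did not know their drug. They will know it. That knowledge can colour what they say in the Ham-D interview and how they rate fatigue on the BFI, of which the plan says: "It is used to assess the severity of fatigue and the interference of fatigue with daily functioning". Fatigue is also an outcome on which the plan expects bupropion to do better.

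Second, the conclusion attached to Hypothesis 1 is stronger than its test. A fall from baseline within one arm mixes drug effect with natural course, placebo response and regression to the mean. Randomisation and the blind rater do not help, because the test makes no comparison between arms. The plan's own Background shows the hazard: open-label fluoxetine studies were positive, while the one placebo-controlled trial failed. Background also says these data are to justify and design a definitive trial, so an efficacy claim made here would feed directly into that decision.

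**Working it through.** **1. Blinding statements side by side.**

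| Place | Statement |
|---|---|
| Section 3, Study Design | open label |
| Section 5, Consent Process | open label |
| Section 6, Research Plan | open label; a rater is blind to medication |
| Analysis section, General Methods | double-blind |

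Three design sections agree with each other. General Methods is the outlier, and no procedure in the document would make it true.

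**2. What the Hypothesis 1 test detects.** Inputs from Determination of Sample Size: N=20 per arm, four post-baseline measures, compound symmetry with r=0.50, d=0.5 SD, alpha 0.05. General Methods makes all tests two-sided.

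Variance of (baseline minus the mean of four post-baseline values), in SD² units:

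1 + (1 + 3r)/4 − 2r = 1 + 2.5/4 − 1 = 0.625, so SD = 0.791

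Standard error with 20 patients: 0.791/√20 = 0.177.

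*Reproducing the plan's power.* Noncentrality = 0.5/0.177 = 2.83. The noncentral t with 19 df, two-sided 0.05, gives 0.765; the plan states 0.78 for the paired t-test. With 76 df, as a mixed model might use, it gives 0.797; the plan's simulation gave 0.79. Both agree within two points.

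*Smallest significant fall.* Critical t (19 df) = 2.093, so 2.093 × 0.177 = 0.37 SD. An observed mean fall of that size or more is significant whatever caused it.

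**3. Illustration with no drug effect at all.** The documents give no size for non-drug improvement, so the shifts below are assumed. The last column squares the per-arm figure, taking the arms as independent with the same shift.

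| Assumed non-drug improvement | Noncentrality | Significant, one arm | Significant, both arms |
|---|---|---|---|
| 0.2 SD | 0.2/0.177 = 1.13 | 19% | 4% |
| 0.3 SD | 0.3/0.177 = 1.70 | 36% | 13% |
| 0.5 SD | 0.5/0.177 = 2.83 | 77% | 59% |

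The 0.5 SD row is the plan's own power calculation. The arithmetic is the same whether the drug or something else produced the change.

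**4. What the limitations say.** Limitations and Alternative Design discusses peripheral rather than CSF measures, the HPA axis and TNF-α antagonists. It mentions neither open-label treatment nor the lack of a placebo or untreated control.

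**The case against.** The best defence is that this is a disclosed pilot whose text is mostly careful. Several parts of it stand.

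- Section 1 predicts a reduction in symptoms from baseline, and Determination of Sample Size frames Hypothesis 1 as within-group improvement. Both are supportable and need no edit. Testing Hypothesis 1 also qualifies *efficacious* by reference to Ham-D change over time.
- The balance sentence and the causal sentence rest mainly on randomisation, which the trial has. A reader might infer that the blinding error undermines baseline balance or voids the between-arm comparison. The documents do not support that.
- Both arms receive an active antidepressant, so bias in Hypothesis 2 needs expectation to differ between arms. Open-label treatment allows this but does not establish it.

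Other strong readings also go beyond the documents:

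- *The blind rater fully protects the Ham-D, leaving only the BFI exposed.* Section 6 names the rater and a study physician jointly for several tasks and does not say who rates what. Patients who know their drug also answer the Ham-D interview. Nor does the plan say that the BFI is self-completed, although it does say so of the pain scale.
- *Regression to the mean inflates Hypothesis 1 by a known amount.* The plan does not say how many candidates fall below the entry cut, or whether the entry and baseline Ham-D scores are the same measurement. No useful figure follows.
- *Expectation gives the BFI comparison a calculable false-positive rate.* The size of any expectation difference is not given. General Methods applies Holm-Bonferroni as necessary without defining the family, so an unadjusted rate would mislead.

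Pilot status does not turn a change from baseline into efficacy, and the words in Aim 1, Hypothesis 1 and Testing Hypothesis 1 remain too strong.

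**Conclusion.** Both points hold and should be corrected. General Methods contradicts three design sections on blinding. The consequence is limited to how far the Hypothesis 2 comparisons appear protected from patients knowing their drug. The efficacy wording of Aim 1 and Hypothesis 1 goes beyond a test that has no control. The design supports a within-arm change in each arm and a randomised comparison of the two drugs; it does not show the absolute efficacy of either.

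The Hypothesis 1 percentages show how the test behaves and do not predict this trial's result. They rest on the plan's r=0.50 and N=20 and on assumed shifts. A reader might infer that the power calculation is wrong; it is not, since the stated 0.78 and 0.79 reproduce closely. They are power to detect a change from baseline, not a drug effect against a control.

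**What to change.** 1. In General Methods, replace the double-blind wording with: *Random, open-label assignment, with a rater blind to study medication*. Add that causal conclusions rest on the randomised between-arm contrasts, which compare the two drugs and do not show the absolute efficacy of either.
2. In Aim 1, Hypothesis 1 and Testing Hypothesis 1, replace *efficacy* and *efficacious* with neutral wording of the same test, for example: *Ham-D will fall from baseline in each arm*, reported with a 95% CI. Keep the contrast as a hypothesis test, so that the power statement still applies. Section 1 stays as it is.
3. In Limitations and Alternative Design, add open-label treatment and the lack of a placebo or untreated control.

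The cost is wording only. No patients, visits, analyses or power figures change. The downside is that the Aim 1 conclusion becomes more modest.
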